	dose commencing on maintenance tofacitinib therapy.
Primary objective	To identify biochemical and genetic markers predictive of
	ulcerative colitis flare
Secondary objective (s)	To identify clinical and disease characteristics predictive
	of ulcerative colitis flare
Number of Subjects/Patients	50 patients
Trial Design	Prospective observational study
Endpoints	1. Flare requiring drug discontinuation, surgery
	(colectomy) or addition of new therapy for ulcerative
	colitis.
	2. Endoscopic activity at week 44 endoscopy
Main Inclusion Criteria	Ulcerative colitis patients commencing tofacitinib
	maintenance dosing, undergoing endoscopy as part of
	their routine clinical care.
Statistical Methodology and Analysis	Receiver operator curves will be generated to determine
	optimal cut-offs for continues variables, predictive of
	disease flare.
	Kaplan-Meier curves will be generated to allow
	comparisons of subdivisions of patients based on genetic
	and biochemical variables, using determined cut-offs.
	Univariate and Multivariate analyses will be performed on
	clinical, biochemical and genetic variables to establish
	predictors of disease flare.

5 Introduction

Tofacitinib has been shown in large-scale randomised clinical trials to be an effective treatment for patients with moderate to severe UC that is resistant to both conventional treatment and to biologic therapy¹. In the few months it has been available in the UK, our unit has accrued some of the biggest experience in the country. Our initial experience and prospectively collected observational data suggest that the drug performs at least as well as clinical trial results would indicate.

Results from the OCTAVE clinical trial program led to the approval of an induction regimen of 10mg BD, with subsequent dose reduction in responders to 5mg BD after at least 8 weeks. This maintenance regimen was shown to maintain remission with greater efficacy than placebo¹. However, the clinical trial data further suggests that in patients who have previously failed anti-TNF therapy, the 10mg BD maintenance dose is superior to the 5mg BD dosing¹. Anecdotally, many clinicians are accordingly favouring continuing the 10mg bd dose in higher risk patients (biologic failures) for up to 52 weeks, rather than dropping to the maintenance dose at week 8.

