Changes in immune homeostasis that predict relapse following dose reduction are most likely to be identified at the site of inflammation. The distinctive molecular changes that underlie the loss of immune homeostasis prior to relapse can be identified by studying gene expression changes in colonic tissue, as has previously been done to predict response to infliximab treatment¹⁵. We wish to compare gene expression changes between patients who remain symptomless on the lower dose of tofacitinib with those patients who ultimately show clear clinical signs of relapse. We expect that the differential gene expression (DEG) list may contain negative regulators of cytokine signaling (SOCS proteins) and/or inhibitors of STAT proteins (PIAS proteins), whose activity critically regulates the functional activation of STAT proteins and downstream cytokine induced gene expression. These studies will identify genes that can be used as biomarkers for relapse following tofacitinib dose decrease and also help in identifying genes that can be more rapidly screened in blood for the purpose of predicting relapse in patients in the clinic.

NHS Foundation Trust

4: Using immune monitoring of the mucosal immune system to identify biomarkers of relapse and remission.

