We have the opportunity to systematically collect tissue from patients with UC treated with tofacitinib, as such we will undertake to track the mucosal immune response by multiparametric flow-cytometry study on endoscopic biopsies of the 50 patients within the BRITE study. These biopsies will be excess to these required to undertake the agreed experiments as part of the original study proposal – hence this proposal is of added benefit and will not detract from the funded study. This will facilitate flow cytometric immune monitoring of the architecture of the mucosal immune system (T cells, B cells and the myeloid compartment) at the point of de-escalation. Patients will subsequently be followed to relapse or the end of the study, whichever comes first, and tissue resampled to investigate the longitudinal changes in immunophenotype in the context of response to therapy. Similar immune monitoring has proved crucial at defining immune signatures in SARS-CoV-2 infection (15). This study is complementary to the work being performed in the original BRITE proposal and will provide more information on the effect of the drug on immunophenotypes and identify immunological signatures of response and or relapse – allowing a precision approach to drug selection.

6 Trial objectives and purpose

This is an investigator-initiated study with an overarching objective to identify biochemical and genetic markers of patients more likely to flare after tofacitinib dose reduction. It is hoped that this will eventually allow us to target continued higher dosing of 10mg bd at those patients who are most likely to benefit from it and avoid its use in patients in whom it is potentially unnecessary. Thereby, it would enable using the drug in a safer, more effective and more economical manner.

Primary objective:

• To identify biochemical, histologic and genetic markers predictive of ulcerative colitis flare in patients on tofacitinib commencing on maintenance 5mg BD dosing.

Secondary objectives:

- To identify clinical characteristics predictive of ulcerative colitis flare in patients on tofacitinib commencing on maintenance 5mg BD dosing.
- To identify predictors of endoscopic activity at week 44

7 Study design & Flowchart

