7.1 Study Design

This is a prospective observational study. We will prospectively enroll a cohort of 50 UC patients who have achieved an adequate response to tofacitinib at a dose of 10mg bd and whose dose is being reduced to 5mg bd following a routine flexible sigmoidoscopy. Colonic

tissue and blood samples will be collected at study entry, and patients' disease course will be followed-up through routine care.

Week 44 has been chosen for the primary endpoint, as 44 weeks post dose de-escalation was used as the endpoint in OCTAVE Sustain.

Primary endpoint:

• Biomarkers, clinical markers and histological markers associated with ongoing treatment with 5mg bd in the absence of steroids at week 44.

Secondary Endpoints

• Biomarkers, clinical markers and histological markers associated with steroid free endoscopic remission at routine endoscopy at week 44

Biomarkers / outcome measures will include:

- Clinical status (SCCAI)
- CRP and faecal calprotectin (as part of routine care)
- Histological markers of disease activity (Nancy histological index) (as part of routine care)
- STAT activation in peripheral blood mononuclear cells
- Cytokine expression in peripheral T cells
- Gene signatures in colonic biopsies

Guy's and St Thomas' MHS

NHS Foundation Trust

Flow Diagram

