9.3 Schedule of Assessment for each visit

Patients in whom the treating team is planning to reduce their Tofacitinib from 10mg BD to 5mg will be referred for consideration of inclusion in the study.

- 1. Screening phone call
 - a. Information regarding the study provided
 - b. Inclusion/exclusion criteria reviewed
 - c. Patient information sheet, and consent form sent to patient in the mail or via e-mail.
- 2. Routine baseline endoscopy
 - a. Informed consent gained and form signed, prior to the endoscopy.
 - b. Baseline clinical data collected
 - c. Endoscopy performed and biopsies taken from rectum and sigmoid, to be sent for:

Guy's and St Thomas' Miss

NHS Foundation Trust

- i. Histological assessment of disease activity (Nancy Histological Index)
- ii. Genetic analysis
- iii. Future exploratory analysis
- d. Blood collection, to be sent for:
 - i. Routine clinical bloods (FBC, CRP, LFTs, U&E)
 - ii. STAT activation in peripheral blood mononuclear cells
 - iii. Cytokine expression in peripheral T cells
- e. Faecal calprotectin submitted
- 3. Flare (SCCAI \geq 5)
 - a. Should a clinical flare occur, patients will be encouraged to contact our IBD advice line as per current standard of care.
 - b. Routine and study blood tests, stool, and endoscopic tests will be initiated, as per standard of care, and the decision on how to manage the clinical flare will be taken by the treating team. Additional study biopsies will be taken at the time of the endoscopy.
- 4. Routine clinical visits
 - a. These will occur as per the treating team's discretion, with testing performed accordingly.
- 5. Week 44
 - a. In patients who remain on tofacitinib at week 44, routine clinical assessment will occur.
 - b. Tests performed will be
 - i. Routine endoscopy and biopsies, sent for:
 - 1. Histological assessment of disease activity (Nancy index) (part of routine care)
 - ii. Study biopsies, sent for:
 - 1. Genetic analysis
 - 2. Future exploratory analysis
 - iii. Routine blood collection, to be sent for:
 - 1. Routine clinical bloods (FBC, CRP, LFTs, U&E)
 - 2. Study blood tests will also be taken at this time point
 - iv. Routine faecal calprotectin

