13.1 Data to be collected

Data will be collected by the study investigators.

Data at the various time points include:

- Baseline:
 - Demographic data, disease extent history, concomitant medications, previous IBD medications, smoking history from patient history and notes.
 - Simple Clinical Colitis Activity Index (SCCAI), calculated by the assessor •
 - Serum CRP and albumin, and faecal calprotectin
 - Endoscopic Mayo Score, recorded by the endoscopist
 - Nancy histological index, reported by the pathologist •
 - STAT activation in peripheral blood mononuclear cells, recorded from • laboratory data
 - Cytokine expression in peripheral T cells, recorded from laboratory data
 - Gene and T/B cell receptor analysis in colonic biopsies, recorded from laboratory data
- Flare
 - Time point, alteration to treatment, faecal calprotectin, CRP, SCCAI, endoscopic Mavo score (if endoscopy performed), all recorded by the investigator from the patient notes.
 - Gene signatures in colonic biopsies, recorded from laboratory data
- Week 44
 - CRP, albumin, SCCAI, calprotectin, recorded from the patient's notes. •
 - Endoscopic Mayo score, recorded by the endoscopist
 - Nancy histological index, reported by the pathologist
 - STAT activation in peripheral blood mononuclear cells, recorded from laboratory data
 - Cytokine expression in peripheral T cells, recorded from laboratory data
 - Gene signatures in colonic biopsies, recorded from laboratory data

In the event of incomplete data, patients will be telephoned to arrange completion.

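### The primary endpoint in 7.1 is a status at week 44, so a patient who flared, was treated on 5mg bd and is steroid-free by then counts as a success, against the protocol's own flare objective

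*Protocol*

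**What the plan says.** Section 7.1 contains the only endpoint labelled primary: markers associated with "ongoing treatment with 5mg bd in the absence of steroids at week 44". The time point is deliberate: "Week 44 has been chosen for the primary endpoint, as 44 weeks post dose de-escalation was used as the endpoint in OCTAVE Sustain".

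Elsewhere the target is flare or relapse as an event:

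- Section 6, primary objective: "To identify biochemical, histologic and genetic markers predictive of ulcerative colitis flare in patients on tofacitinib commencing on maintenance 5mg BD dosing".
- Section 5, question 3, sets the gene-expression comparison as "patients who remain symptomless on the lower dose of tofacitinib with those patients who ultimately show clear clinical signs of relapse".
- Section 4, first endpoint: "Flare requiring drug discontinuation, surgery", continuing with "colectomy) or addition of new therapy for ulcerative" colitis.
- Section 14.2 directs the ROC cut-offs and the univariate and multivariate models at disease flare.

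Section 9.3 defines flare as SCCAI ≥ 5 and states that "the decision on how to manage the clinical flare will be taken by the treating team". It schedules the week-44 assessment for everyone still on tofacitinib, whether or not they flared earlier. Section 13.1 lists, at flare, "Time point, alteration to treatment, faecal calprotectin, CRP, SCCAI" among the items recorded.

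**The concern.** The 7.1 rule asks two things on one date: is the patient on 5mg bd, and is the patient off steroids? It does not ask what happened between dose reduction and that date. A flare that was treated and settled therefore leaves no trace in the outcome. Nor does the rule mention non-steroid therapy, so a patient still taking one added for a flare also qualifies.

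The study exists to separate patients who relapse after dose reduction from those who do not. If some relapsers are counted with the non-relapsers, a marker that truly predicts relapse shows a smaller difference between the groups. With 50 patients there is little room for that loss. Choosing 7.1 over the synopsis as the single definition would not help, because the gap lies in the period the 7.1 rule covers.

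**Working it through.** **Step 1: apply each definition to the same patient.** The three courses below are hypothetical.

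| Course after dose reduction | 7.1 status | Sections 5, 6 and 14.2 | Section 4 endpoint |
|---|---|---|---|
| (a) Flare at week 10, steroids while on 5mg bd, off steroids at week 18, on 5mg bd at week 44 | Success | Flare / relapse | Event only if a steroid course counts as new therapy; not stated |
| (b) Flare at week 20, non-steroid therapy added to 5mg bd and continued to week 44 | Success | Flare / relapse | Event |
| (c) Flare at week 15, re-escalated, reduced again before week 44 | Depends on whether ongoing means uninterrupted; not defined | Flare / relapse | Not determined by the wording |

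Courses (a) and (b) are enough to show the conflict. No other section removes these patients from the 7.1 success group. The statement in section 5 that patients are followed to relapse or study end describes the mucosal immune work and is not a scoring rule for 7.1.

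**Step 2: how many flares could be misscored.** The protocol gives no flare rate, steroid-use rate, effect size or power, so there is no figure to reproduce and every input here is an assumption. Take flare times uniform over 44 weeks and a steroid course of c weeks.

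- Share of courses finished by week 44 = (44 − c)/44. For c = 8: 36/44 = 0.82. For c = 12: 32/44 = 0.73.
- If a share s of flares is treated this way on 5mg bd, the misscored share is s × (44 − c)/44. Low end: 0.20 × 0.73 = 0.145. High end: 0.50 × 0.82 = 0.41.
- With 40% flaring (20 of 50), that is 20 × 0.145 = 2.9 to 20 × 0.41 = 8.2, or about 3 to 8 patients.

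**Step 3: effect on a marker with true AUC 0.75.** If k flared patients join the 30 true non-flarers, and they carry the same marker level as other flarers, the expected AUC is (30 × 0.75 + k × 0.50)/(30 + k). Power is for a two-sided 5% Mann-Whitney test, by simulation with normal markers.

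| Misscored share | k | Expected AUC | Power |
|---|---|---|---|
| 0 | 0 | 0.75 | 0.88 |
| 0.145 | 2.9 | 0.73 | 0.78 |
| 0.29 | 5.8 | 0.71 | 0.66 |
| 0.41 | 8.2 | 0.70 | 0.53-0.54 |

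If patients who recover have marker levels halfway between the two groups, power falls only to about 0.82 at the low end and 0.66 at the high end.

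**Step 4: a second method.** Compare two means with a true difference of 0.8 SD, N = 50 and two-sided 5%, with flare share f and share s of flared patients who meet the 7.1 status. Contamination of the success group is f·s/(1 − f + f·s), and the difference shrinks by one minus that. For f = 0.40 and s = 0.25: 0.10/0.70 = 0.143, and 0.8 × 0.857 = 0.686 SD. Power falls from 0.79 to 0.60. Over f = 30-50% and s = 10-40%, 1.5 to 10 patients are misscored, and power falls from 0.74-0.81 to 0.46-0.73. The size of the loss is similar.

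**The case against.** The strongest reply is that section 14.2 does not analyse the 7.1 status. Its ROC curves and regression models address disease flare, as does the primary objective, and a week-10 flare is a flare whatever happens later. This stands. A reader might infer that the planned analysis will lose the power shown above, but the documents do not support that. The loss arises only if the 7.1 status is the outcome analysed. What remains is that the one endpoint labelled primary classifies patients differently from the analyses meant to serve it.

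Other points on that side:

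- A re-escalated and later reduced patient, course (c), may not be on ongoing 5mg bd. This is a fair reading, so the point does not rest on that case.
- The synopsis already makes added therapy for a flare an event. This is true, but it means two sections score course (b) in opposite ways.
- A landmark at week 44 has a stated rationale and is a defensible outcome for durable maintenance. That supports keeping it as an endpoint. It does not make it a measure of flare.
- An SAP might settle how interim treatment is handled. It could add detail, but the protocol has itself fixed a primary endpoint that conflicts with its objective.
- The study is exploratory, and section 14.1 makes no power claim. This limits the weight of the figures.

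Two further inferences should be avoided. That markers of early relapse are diluted most would require early and late flares to be equally likely to settle on 5mg bd, which no section states. The recapture figures in section 5 (64.9% and 49.1%) concern re-escalated dosing, so they do not estimate recovery on 5mg bd.

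**Conclusion.** The point holds as an endpoint definition that contradicts the protocol's own objective, intended contrast, synopsis endpoint and analysis section. On the wording of 7.1, a patient who flared and was treated while staying on 5mg bd is a success if steroid-free at week 44.

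The consequence for marker detection is conditional on the 7.1 status being the analysed outcome. Its size cannot be derived from the documents. The fall in power from about 0.88 to about 0.78-0.53 assumes 20 flares in 50 patients, a true AUC of 0.75, uniform flare times, 8-12 week steroid courses, and 20-50% of flares treated this way on 5mg bd. It also assumes that recovered patients resemble other flarers on the marker. With intermediate marker levels the loss is smaller. This should be corrected, in proportion to an exploratory study.

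**What to change.** Restate the primary outcome in 7.1 as flare-free, steroid-free continuation of 5mg bd from dose reduction through week 44, or as time to first flare. In either form:

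- Count as an event, at any time up to week 44, a flare (SCCAI ≥ 5, as in 9.3), or a steroid course, re-escalation, new ulcerative colitis therapy or colectomy for flare. Flare itself must be on the list. Otherwise a flare managed without those steps would still be a success.
- Classify stops of 5mg bd for reasons other than flare separately, for example as censored in a time-to-flare analysis, so that they do not enter the relapse group.
- Count only steroid courses started after dose reduction, because 8.1 and 8.2 do not exclude steroid use at entry.

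Keep the week-44 status as a supportive endpoint, and align sections 4, 6, 7.1 and 14.2 to one outcome.

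These are scoring rules only and change nothing in care or visits. Flare time and treatment alteration are already recorded under 13.1. However, treatment change is listed there only under flare, so the notes must also be checked for changes between visits. The success proportion will be somewhat lower and less comparable with week-44 status figures, which is the reason for keeping that status as supportive.

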Inevitably, our early experience is in a largely anti-TNF and vedolizumab experienced cohort; nonetheless, response rates appear to be favourable. The decision to dose reduce these patients must be carefully considered, particularly in view of their previous biologic failures and hence limited options should they fail tofacitinib. Recent extension studies from the original clinical trials have shown that only 64.9% and 49.1% of patients who flare after dose de-escalation are able to recapture response and remission, respectively, on dose re-escalation².

The risk of flare with dose reduction needs to be balanced against the potential risk of continuing at the 10mg bd dose. There is a clear dose response in terms of the risk of herpes zoster^{1,3,4}, and recent communication from a trial of patients with rheumatoid arthritis has suggested that there may be other safety signals in the form of greater risk of venous thromboembolism with the higher dose².

Therefore, given that many patients who are receiving tofacitinib will be biologicexperienced, there is an urgent need to identify biomarkers that might predict those more likely to flare should they dose reduce. Such biomarkers would enable us to risk stratify our patients at the point of consideration of dose reduction, to enable assessment of the risk and benefit of dose reduction versus continuation at the higher dose. By extension, predictors would enable us to maintain higher dosing in those more likely to flare with dose reduction, justifying the additional risk. To the best of our knowledge, there is neither any data already in existence that addresses this field, nor are there any ongoing trials. As IBD enters the era of personalised/precision medicine, gaining a deeper understanding of the best use of our most efficacious agents, such as tofacitinib, appears an essential endeavour.

This study aims to explore 3 novel areas for predictive biomarkers, in addition to assessing the predictive capability of baseline (defined here as the point of dose reduction) clinical, endoscopic and histologic markers. We hypothesize that patients who relapse following dose reduction to maintenance dose tofacitinib will have changes in cytokine expression of their pro-inflammatory effector T cells in peripheral blood mononuclear cells (PBMCs), increased

STAT activation in PBMCs, and possibly signature genes in their colonic tissue that may predict relapse. Accordingly, we aim to address 3 novel questions:

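### The week-44 endoscopic endpoint omits the 5mg bd condition of the primary endpoint, so patients who flare, are re-escalated and heal off steroids count as remission

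*Protocol*

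**What the plan says.** Section 7.1 sets two week-44 endpoints, one directly after the other. The primary concerns markers "associated with ongoing treatment with 5mg bd in the absence of steroids at week 44". The secondary concerns "Biomarkers, clinical markers and histological markers associated with steroid free endoscopic remission at routine endoscopy at week 44", with no dose condition and no condition on what happened between dose reduction and week 44.

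The other statements of the endoscopic outcome set no dose condition either. The synopsis (section 4) has "Endoscopic activity at week 44 endoscopy" and the secondary objective (section 6) has "To identify predictors of endoscopic activity at week 44".

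Section 9.3, item 5, decides who is assessed: "In patients who remain on tofacitinib at week 44, routine clinical assessment will occur". The dose is not specified. Item 3 of the same section leaves the management of a flare to the treating team.

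The introduction (section 5) reports that "only 64.9% and 49.1% of patients who flare after dose de-escalation are able to recapture response and remission, respectively, on dose re-escalation". The overarching aim in section 6 is to "identify biochemical and genetic markers of patients more likely to flare after tofacitinib dose reduction".

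**The concern.** The study asks which patients can hold their response on the reduced dose. A patient who relapsed on 5mg bd and was recaptured on a higher dose belongs on the unfavourable side of that question. As the secondary endpoint is worded, the same patient is on the favourable side if the week-44 endoscopy shows remission off steroids. The introduction cites a recapture rate after re-escalation, so the authors knew of this route.

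This differs from missing data. Patients who stop tofacitinib may have no week-44 endoscopy. The patients at issue here do have one, and the wording places them with those who never relapsed. If markers differ between maintained and relapsing patients, mixing the two in one group tends to shrink the contrast for this endpoint.

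**Working it through.** The protocol gives no sample size calculation and no expected rate for this endpoint, so there is no stated figure to reproduce. The check has a textual part and an illustration of size.

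**Text: one patient followed through the definitions.** The patient flares, is re-escalated, and at week 44 is on the raised dose, off steroids and in endoscopic remission.
- Primary endpoint (7.1): not met, because the patient is not on 5mg bd.
- Week-44 assessment (9.3, item 5): takes place, because the patient is still on tofacitinib.
- Secondary endpoint (7.1): met, because the patient is steroid-free and in endoscopic remission.
- No section says that such a patient is classified differently.

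**Size: inputs.**
- From the protocol: N = 50 (sections 4 and 7.1) and 49.1% recapture of remission (section 5). The 49.1% is not stated to be endoscopic, steroid-free or at week 44.
- Assumed: flare rate f = 30–50%, share of flares re-escalated r = 50–90%, share of non-flarers in steroid-free endoscopic remission s = 70–90%.

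**Formulas.**
- Re-escalated remitters R = 50 × f × r × 0.491
- Non-flaring remitters M = 50 × (1 − f) × s
- Share of the remission group = R / (R + M)

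**Results.**

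| f | r | s | R | M | Share | Remission rate as written | Rate requiring 5mg bd |
|---|---|---|---|---|---|---|---|
| 30% | 50% | 90% | 3.7 | 31.5 | 10.5% | 70.4% | 63.0% |
| 40% | 70% | 90% | 6.9 | 27.0 | 20.3% | 67.7% | 54.0% |
| 40% | 70% | 70% | 6.9 | 21.0 | 24.7% | 55.7% | 42.0% |
| 50% | 90% | 70% | 11.0 | 17.5 | 38.7% | 57.1% | 35.0% |

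For the middle rows, R = 50 × 0.4 × 0.7 × 0.491 = 6.9, and 6.9 / (6.9 + 27) to 6.9 / (6.9 + 21) gives 20.3% to 24.7%.

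**Direction of the effect on a marker.** Take a hypothetical marker with 60% flare in positives and 20% in negatives. Suppose all flares are re-escalated, recapture is 49.1% whatever the marker, and every non-flarer is in remission. If 5mg bd is required, remission is 40% v 80%, a difference of 40 points. As written it is 0.40 + 0.60 × 0.491 = 69.5% v 0.80 + 0.20 × 0.491 = 89.8%, a difference of about 20 points. These assumptions sit at the severe end. The example shows the direction and is not a forecast.

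**The case against.** The strongest reply is that endoscopic remission on any treatment is a legitimate secondary outcome. Both the objective in section 6 and the synopsis speak only of endoscopic activity at week 44, so requiring 5mg bd is a choice of estimand, and it makes the secondary endpoint a subset of the primary. This stands in part: the any-dose outcome is worth reporting. But the protocol never says it is intended, it sits poorly with the aim in section 6, and section 5 frames its gene-expression comparison around patients who stay symptom-free on the lower dose.

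A second reply is that the data would allow reclassification at analysis. Section 13.1 already records when a flare occurred and how treatment was altered. This also stands in part. However, the week-44 list in 13.1 names neither tofacitinib dose nor steroid use, and dose changes outside a recorded flare are not listed. A SAP could refine the handling, but the dose condition is part of an endpoint that the protocol itself defines.

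Third, section 5 (question 4) follows patients to relapse or study end, and sections 8 and 10 place the second study sample at flare or week 44, so flared patients might never reach week 44. The first statement belongs to the immune-monitoring add-on, and the others concern study samples and study-specific tests. None limits the routine endoscopy in 9.3.

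The third reply does defeat one tempting inference, that the week-44 research samples necessarily mix two doses. Sections 8 and 10 suggest that flared patients give their second sample at flare, so the documents leave this open.

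**Conclusion.** The point holds for the secondary endpoint. As worded, it counts some patients who relapsed on 5mg bd as favourable. Under the stated assumptions this is about 4 to 11 of 50 patients, or 10–39% of those counted as in remission. The flare, re-escalation and non-flarer remission rates are assumptions, and the 49.1% is borrowed for an outcome it is not stated to measure, so the figures show scale only.

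Three stronger readings are not supported:
- **That the protocol labels these patients a success of dose reduction.** It does not use that label. The mismatch is inferred from the study's aim.
- **That the study's relapse findings are diluted generally.** The primary endpoint requires 5mg bd, and the cut-off and predictor analyses in section 14.2 target disease flare. The synopsis endpoint beginning "Flare requiring drug discontinuation, surgery" does not name re-escalation, which is a reason to align the wording. It does not carry the gap in the endoscopic endpoint into the flare analyses.
- **That a marker's AUC falls by a given amount.** A calculation such as 0.75 − 0.25 × share treats the non-remission group as relapsers only. With 40% flare and 70–90% remission in the 30 non-flarers, 3 to 9 non-flarers are also in that group, so 0.75 is not the right starting value. No specific AUC loss is established.

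The endpoint is secondary and the endpoints are declared exploratory. Severity: should-fix.

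**What to change.** For analysis purposes:
- Define the main secondary endpoint as steroid-free endoscopic remission at week 44 while still on 5mg bd, with no re-escalation or added ulcerative colitis therapy since dose reduction. Count re-escalated patients as not meeting it.
- Report steroid-free endoscopic remission on any dose alongside, labelled as such.
- Add to section 13.1 the tofacitinib dose and steroid use at week 44, and the dates of dose changes made outside a recorded flare.
- Align the endpoint wording in the synopsis, section 6 and section 7.1.
- Reconcile section 9.3 with sections 8 and 10 on whether patients who have flared have week-44 assessments and study samples.

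The cost is endpoint wording and a few fields taken from routine notes. The reported remission rate for the main definition will be lower. The change affects outcome classification only and implies nothing about how flares are managed.
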